Post-intensive care syndrome (PICS) is a common consequence of an intensive care unit (ICU) stay and can last up to 5 years.[1–3] The family members are often affected, reporting diminished quality of life and mental health related quality of life.[4] About 80% of family members become informal carers and 33% of families

see a significant reduction of income the first 6 months after discharge.[5] The extent to which these problems will be modified by the pandemic and coronavirus disease 2019 (COVID-19) remains unknown.

If under normal circumstances, an ICU stay has detrimental effects, the pandemic added two extra factors. Firstly, a rapid and exponential increase in acute care bed capacity might have affected the quality of care delivered by spreading too thin highly skilled healthcare staff. Secondly, COVID-19 involves a new disease with great uncertainties regarding treatment, prognosis and long-term effects. Early reports suggest that 64% of patients who were discharged from ICU after severe COVID-19 have at least one symptom of PICS at 6 months after discharge[6] and 32% had anxiety or depression symptoms,[7] which suggests these patients will have similar impairments to what has been reported for other ICU survivors previously.[8,9] Additionally, infection control protocols meant that healthcare staff had to wear personal protective equipment and family visiting was restricted.[10] These factors add another layer of potential negative effects due to challenges in communication with patients and their family members. Therefore, we hypothesize that the prevalence and severity of mental, physical, and cognitive impairments will be higher in patients treated in periods of higher bed occupancy and those who had severe COVID-19. In the case of family members, we expect that the experience of having a next of kin in the ICU during pandemic would be stressful and traumatic, but those with social support will cope better. In the case of staff members, their experiences will vary greatly depending on their profession and workplace, but we expect places with a more open/ less hierarchical structure to have coped better with the increase in demand.

The primary objective of this study is to compare the trajectory of mental, physical and cognitive impairments at ICU discharge, 3 and 6 months of mechanically ventilated adult patients who survived an ICU stay due to severe COVID-19 or other causes, during the pandemic. Secondary objectives are:

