Hodgson et al (2017) found that a quarter of ICU survivors had severe or moderate disability at 6 months after discharge, and half of them had mild disability.[8] There is no information to estimate how much the prevalence of disability increases during a pandemic; however, the prevalence of mental health issues could be used as a proxy of the expected impact on physical health. Hodgson et al (2017) found that 22% of patients had anxiety or depressive symptoms at 6 months after discharge. Lee et al (2007) found that among survivors of the SARS outbreak, 40% had at least moderate anxiety one year after.[42] This is equivalent to a relative risk of 1.81. Considering that measurement time points are different, we have estimated our sample size assuming a relative risk (RR) of 1.5 or 1.6, which is more conservative than the estimation based on the literature. The different scenarios used for the sample size calculation appear in **Table 3**.

Table 3. Different plausible scenarios for sample size calculation

Outcome	Risk in non-pandemic situation	Risk during the pandemic	Type 1 error	Power	Sample size
WHODAS 2.0	25% severe or moderate disability	40% severe or moderate disability (RR=1.6)	0.05	0.8	343

WHODAS 2.0	40% some degree of disability	64% some degree of disability (RR=1.6)	0.05	0.8	288
WHODAS 2.0	50% mild disability	75% mild disability (RR=1.5)	0.05	0.8	388
HADS	22% anxiety or depressive symptoms	40% moderate anxiety (RR=1.8)	0.05	0.8	226

HADS, Hospital Anxiety and Depression Scale; WHODAS, World Health Organization Disability Assessment Schedule; RR, relative risk

The most plausible scenario is that 40% of ICU survivors discharged in a low demand period will have some degree of disability and this will increase to 64% for those discharged during high-demand periods. Considering loss to follow-up, we estimate 550 patients need to be recruited at ICU discharge; so 413 patients are assessed at 3 months after discharge (25% loss to follow-up) and 289 patients at 6 months (30% lost to follow-up).

Quantitative analysis

Categorical variables will be presented as absolute and relative frequencies for each subgroup (i.e. admission diagnosis and treatment centre) and time point (i.e. ICU discharge, 3 and 6 months follow-up). In the case of normally distributed continuous variables, these will be summarised using the mean and standard deviation, while for those non-normally distributed, the median and interquartile range will be used instead.

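### The Table 3 HADS row uses the undiscounted relative risk of 1.8, although the text says the sample size assumes 1.5 or 1.6; at the text's own figures HADS has about 50–70% power at 289 patients

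*Combined protocol and SAP*

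**What the plan says.** Under Sample size calculation, the starting point is a study of general ICU survivors in which "22% of patients had anxiety or depressive symptoms at 6 months after discharge", set against 40% with at least moderate anxiety one year after SARS. The text adds: "This is equivalent to a relative risk of 1.81". It then gives a reason for not using that ratio as it stands, "Considering that measurement time points are different", and says the sample size was estimated "assuming a relative risk (RR) of 1.5 or 1.6, which is more conservative than the estimation based on the literature".

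Table 3 lists four scenarios. The three WHODAS 2.0 rows use 1.6, 1.6 and 1.5. The HADS row sets "22% anxiety or depressive symptoms" against "40% moderate anxiety (RR=1.8) 0.05 0.8 226", where the last three entries are type 1 error, power and sample size.

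The recruitment target comes from the WHODAS 2.0 row of 40% against 64%, called the most plausible: 550 recruited, 413 assessed at 3 months and 289 at 6 months. WHODAS 2.0 at 6 months is the primary outcome and HADS is secondary. Mental impairment is nevertheless named in the primary objective, and the Quantitative analysis section says HADS will be analysed as categories as well as total scores.

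**The concern.** The text states a rule and the table departs from it for one outcome. That outcome is the one whose data produced the 1.81, so the reason given for the discount (6 months against one year) applies to it most directly. The row also pairs anxiety or depressive symptoms on one side with moderate anxiety on the other, which is a further reason not to take the ratio at face value.

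A reader who sees 226 in the HADS row and 289 planned at 6 months will conclude that HADS is powered with room to spare under the discounted assumption. If it is not, a null HADS result could be read as evidence of no difference when the study had limited ability to show one. The same risk arises for moderate or severe disability, whose Table 3 row asks for more patients than are planned at 6 months.

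**Working it through.** **Inputs from the plan.** HADS row: 22%, 40%, type 1 error 0.05, power 0.8, total 226. Text: relative risk 1.5 or 1.6. Planned number at 6 months: 550 × 0.75 × 0.70 = 288.75, i.e. 289.

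**Assumptions, because the plan does not state them.** Two-sided test; equal groups, with 2:1 and 3:1 shown as a range; no allowance for clustering by centre.

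**Formulas.** With d = p2 − p1 and p̄ the mean of p1 and p2:

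- Per group: n = [1.960·√(2p̄(1−p̄)) + 0.842·√(p1(1−p1) + p2(1−p2))]² / d²
- With continuity correction: n_c = (n/4)·[1 + √(1 + 4/(n·d))]²
- Power with m per group: Φ{[d − 1.960·√(2p̄(1−p̄)/m)] / √[(p1(1−p1) + p2(1−p2))/m]}. For corrected power, first solve the correction formula for the n that corresponds to m.

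**Step 1: reproduce the printed row.** 0.40/0.22 = 1.818. With p̄ = 0.31 and d = 0.18, n = (1.960 × 0.6541 + 0.842 × 0.6416)² / 0.0324 ≈ 102.5, so 103 per group and 206 in total. With correction, n_c ≈ 113.3, so 114 per group and 228 in total, against 226 printed. The row is reproduced to within 2 patients, and it rests on the undiscounted contrast.

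**Step 2: apply the text's rule.** At 1.6, p2 = 0.22 × 1.6 = 0.352, p̄ = 0.286 and d = 0.132, so n = (1.960 × 0.6391 + 0.842 × 0.6322)² / 0.01742 ≈ 183 per group. At 1.5, p2 = 0.33 and n ≈ 258 per group.

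**Step 3: power at 289 (m = 144.5).** At 1.6: (0.132 − 1.960 × 0.05316)/0.05259 = 0.53, and Φ(0.53) ≈ 0.70. All HADS cases, uncorrected / corrected:

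| HADS contrast from 22% | Total for 80% power | Power at 289 |
|---|---|---|
| 40% (RR 1.82, as printed) | 206 / 228 | 91.5% / 89% |
| 35.2% (RR 1.6) | 366 / 396 | 70% / 65% |
| 33% (RR 1.5) | 516 / 552 | 55% / 50% |

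With unequal groups (replace 2/m by 1/n1 + 1/n2 and weight p̄ by group size; uncorrected), the 2:1 figures are 64–66% at 1.6 and 49–52% at 1.5, depending on which group is larger. At 3:1, with the larger group at the higher risk, they are 55% and 42%.

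**Step 4: the other rows at 289, equal groups, uncorrected.**

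- 25% against 40%: power about 78%. The row prints 343; the formula gives 304, or 330 with correction. All three exceed 289.
- 40% against 64%: power about 98.6%.
- Smallest relative risk detectable with 80% power: 1.68 from 22% (to 37.0%), 1.62 from 25% (to 40.4%) and 1.41 from 40% (to 56.4%).

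The printed totals of the WHODAS 2.0 rows do not come out of the same formula and settings. That is a separate matter, and nothing here relies on them beyond the comparison of 343 with 289.

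**The case against.** The best defence is that Table 3 is a list of scenarios, that the HADS row openly prints its relative risk as 1.8, and that this row does not set recruitment. All of that is true, and it keeps the point small. It does not remove the mismatch, because the text introduces the table as resting on 1.5 or 1.6 and nothing marks the HADS row as an exception.

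The planned analysis is also a longitudinal multilevel regression that uses total scores as well as categories. Its power may differ from that of a two-proportion comparison at 6 months. That stands as a limit on the figures above, although Table 3 is itself built on proportions.

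Three stronger readings are tempting, and the documents do not support them.

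- **That the HADS row fails to deliver its stated power.** At its own 22% against 40% it does deliver: about 80–84% with 226 and 89–91.5% with 289. The shortfall appears only at the smaller effect that the text says it assumes.
- **That calling 1.5–1.6 more conservative is false.** The comparison is with the 1.81 just derived, and against that figure it is correct.
- **That the protocol's own COVID-19 figure implies 1.45.** The Introduction reports that "32% had anxiety or depression symptoms,[7] which suggests these patients will have similar impairments to what has been reported for other ICU survivors previously", and 32/22 = 1.45. The plan never forms that ratio. It crosses two studies: the title of the cited COVID-19 paper refers to patients discharged from hospital, whereas the 22% is for ICU survivors. It also does not estimate the contrast used for sizing, which is low against high demand in the text and non-pandemic against pandemic in Table 3. The same Introduction goes on to hypothesise higher impairment with high occupancy and severe COVID-19. The 32% may serve at most as a sensitivity scenario, with about 48% power at 289 (43% corrected). Even at 1.45 the driving scenario (40% to 58.2%) keeps about 87% power.

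**Conclusion.** The inconsistency is real and minor. Under the rule stated in the text, the HADS row should ask for about 366–396 patients (relative risk 1.6) or 516–552 (1.5) instead of 226, and the planned 289 give about 65–70% or 50–55% power. Moderate or severe disability, a row for the primary outcome measure, has about 78% power at 289 on its own assumptions. The 40% against 64% scenario that sets the target is not affected by this point.

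The figures assume a two-sided 5% test of two proportions at 6 months, equal groups and no clustering. Unequal groups lower them. They also assume 550 recruited. The abstract gives 450, which with the same losses leaves 450 × 0.75 × 0.70 ≈ 236, and HADS power of about 61% (1.6) or 47% (1.5) without correction.

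**What to change.** 1. In Table 3, either recompute the HADS row at 1.5 and 1.6 or label it as the undiscounted literature scenario. State whether the test is two-sided, the group ratio, and whether a continuity correction is used.
2. For each row, add the power or the detectable relative risk at 289. With equal groups the detectable values are about 1.68 from 22%, 1.62 from 25% and 1.41 from 40%.
3. Make no 80% power claim for HADS at the discounted relative risk, or for moderate or severe disability. Say that these will be reported as estimates with confidence intervals.
4. If the 32% is used at all, show it as a sensitivity scenario and say that it is a cross-study comparison.

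The wording that calls 1.5–1.6 more conservative can stay. The cost is one table row, one added column and a sentence or two. The stated figures become less favourable, and recruitment does not change.

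### Two of the four sample sizes in Table 3 do not follow from their stated inputs, and one of them (288) is the basis of the recruitment target

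*Combined protocol and SAP*

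**What the plan says.** The Sample size calculation section gives four scenarios in Table 3, all at type 1 error 0.05 and power 0.8:

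| Row | Outcome | Risks compared | Stated sample size |
|---|---|---|---|
| 1 | WHODAS 2.0, moderate or severe | 25% vs 40% | 343 |
| 2 | WHODAS 2.0, "40% some degree of disability" at baseline risk | 40% vs 64% | 288 |
| 3 | WHODAS 2.0, "50% mild disability" at baseline risk | 50% vs 75% | 388 |
| 4 | HADS | 22% vs 40% | 226 |

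No formula, sidedness, group split or design effect is stated. The paragraph after the table selects row 2: "The most plausible scenario is that 40% of ICU survivors discharged in a low demand period will have some degree of disability". It then says "we estimate 550 patients need to be recruited at ICU discharge", leaving 413 at 3 months after 25% loss and 289 at 6 months after a further 30% loss. The Methods and analysis paragraph of the abstract gives the sample as 450 adults. The primary outcome is WHODAS 2.0 disability at 6 months, so the 6-month number is the one that matters for power.

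**The concern.** The table can be seen to be out of order without any formula. Row 3 compares risks 25 percentage points apart and row 1 risks 15 points apart, at the same alpha and power, yet row 3 is given the larger sample (388 against 343). The easiest contrast is shown as the hardest.

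Two things are at stake. First, the sample size that the study names as its basis, and the 80% power attached to it, may not follow from the risks given. Second, a reader who takes 80% at face value would be misled about which disability question the expected 6-month sample can answer.

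There is also a labelling conflict. Row 2 puts the broad category (any degree of disability) at 40%, while row 3 puts mild disability alone at 50%. As labelled, the broader category cannot be the rarer one.

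**Working it through.** **The plan's attrition chain.** Backwards from 288: 288/0.70 = 411.4, so 412; 412/0.75 = 549.3, so 550. Forwards: 550 × 0.75 = 412.5 (413), and 413 × 0.70 = 289.1 (289). The chain is correct, and it shows that row 2's 288 is the source of both 289 and 550.

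**Formula for the table.** The risks, alpha 0.05 and power 0.80 come from Table 3. Two-sided testing, equal groups and independent patients are assumed, because the plan states none of these. Per group, with p̄ the mean of the two risks and d their difference:

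n = [1.960 √(2p̄(1−p̄)) + 0.842 √(p₁(1−p₁) + p₂(1−p₂))]² / d²

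With continuity correction: n′ = (n/4)[1 + √(1 + 4/(nd))]².

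- Row 2: p̄ = 0.52, d = 0.24. n = (1.385 + 0.577)²/0.0576 = 66.8, so 67 per group and 134 in total. Corrected: 74.9, so 75 per group and 150 in total.
- Row 3: p̄ = 0.625, d = 0.25. n = (1.342 + 0.557)²/0.0625 = 57.7, so 58 per group and 116 in total. Corrected: 65.4, so 66 per group and 132 in total.

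Totals for all rows, uncorrected/corrected:

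| Row | Stated | 1:1 | 2:1 low:high | 4:1 low:high | Stated ÷ 1:1 total |
|---|---|---|---|---|---|
| 1 (25 vs 40) | 343 | 304/330 | 336/366 | 458/499 | 1.13/1.04 |
| 2 (40 vs 64) | 288 | 134/150 | 152/170 | 208/233 | 2.15/1.92 |
| 3 (50 vs 75) | 388 | 116/132 | 132/150 | 184/208 | 3.34/2.94 |
| 4 (22 vs 40) | 226 | 206/228 | 225/251 | 305/339 | 1.10/0.99 |

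Row 4 is reproduced with the correction. Row 1 is near, 4% above the corrected value. Rows 2 and 3 are about twice and three times too large.

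**Could an unstated split or design effect explain it?** A design effect common to all rows cancels when one row is divided by another. Over splits from 1:20 to 20:1, one- or two-sided, with or without correction, the largest attainable ratios are:

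- row 3/row 1: 0.42 (stated 388/343 = 1.13)
- row 2/row 1: 0.47 (stated 288/343 = 0.84)
- row 2/row 4: 0.70 (stated 288/226 = 1.27)

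At 1:1, the design effect that lifts row 2 to 288 is 288/150 = 1.92 or 288/134 = 2.15. The same factor would make row 1 330 × 1.92 = 634 or 304 × 2.15 ≈ 653, and row 4 228 × 1.92 = 438 or 206 × 2.15 = 443.

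Unpooled, arcsine, log relative risk and log odds ratio formulas give 128–147 for row 2 and 110–127 for row 3. Treating the risks as Poisson rates (log rate ratio) gives 288.7 for row 2, but 318 for row 3, 462 for row 1 and 309 for row 4.

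**Power at the expected 6-month number.** If 450 are recruited with the same losses, 450 × 0.75 × 0.70 = 236 remain. Two-sided, no clustering, corrected to uncorrected:

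| Contrast | N | 1:1 | 2:1 low:high | 1:2 | 4:1 low:high | 1:4 |
|---|---|---|---|---|---|---|
| 40 vs 64 | 289 | 98–99% | 97–98% | 97–98% | 89–91% | 89–92% |
| 40 vs 64 | 236 | 95–96% | 92–94% | 92–94% | 81–85% | 81–85% |
| 25 vs 40 | 289 | 74–78% | 70–74% | 68–72% | 56–62% | 50–57% |
| 25 vs 40 | 236 | 64–69% | 60–66% | 57–63% | 47–54% | 41–48% |

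The plan gives no intraclass correlation. As an assumption only, a design effect of 1.4–1.8 at 289 and 1:1 leaves 83–94% for 40 vs 64 and 46–64% for 25 vs 40.

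**The case against.** The best defence is that the error does little harm. The chosen scenario has more than 80% power at every split shown, at 289 and at 236, if clustering is ignored. Recruitment is set by calendar and funding (all eligible patients discharged from October 2020 to April 2021), and 388 is used nowhere else. This stands as a limit on the consequences. It does not make the figures right, and 288 is what the 550 is built on.

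Second, the ratio argument assumes one split and one design effect for the whole table. Row-specific high:low splits of about 5.4–6.8:1 (row 2) and 10–13:1 (row 3) would reach the printed numbers. That is true, but rows 1 and 4 fit splits between about 1:1 and 2:1, and the plan states no split at all. The supportable claim is that no common method explains the table.

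Third, the plan does not commit to row 1, and it prints both 343 and 289, so the shortfall is not hidden. The planned analysis is also a longitudinal multilevel regression, so two-proportion power only approximates it. Both are fair. But the plan itself sized the study on two proportions, and nothing in its text points out that 289 falls short of its own 343.

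Fourth, 450 against 550 is a separate discrepancy, and 236 is conditional on 450 meaning recruits with the same losses. It belongs here only because it changes the number at which power must be stated.

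**Conclusion.** The concern holds. Under two-sided testing with equal, independent groups, 288 should be 134 (150 corrected) and 388 should be 116 (132 corrected). No common split, sidedness, correction or design effect recovers the table.

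For the scenario that the plan selects, the error is conservative: power at 289 is 98–99% at 1:1 and 89–92% at a 4:1 split either way, not 80%. Clustering would lower these figures.

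The misleading part is the ranking. Table 3 shows 50% vs 75% as the most demanding scenario, when it is the least demanding. The most demanding is moderate or severe disability, 25% vs 40%. For it the expected 6-month sample gives 74–78% power at best (289, 1:1, no clustering) and 41–48% at 236 with a 1:4 low:high split. The low:high split and the intraclass correlation are not in the plan, so these figures are ranges over assumptions.

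**What to change.** - Recompute all four rows of Table 3 with one named formula. State sidedness, continuity correction, the expected low:high-demand split, the design effect for seven centres (or that none is used), and that each figure is a total. For equal independent groups the reference totals are 304/330, 134/150, 116/132 and 206/228 (uncorrected/corrected).
- Keep recruitment as planned. Replace the 80% claim with the power of the expected 6-month number for each scenario, at 1:1, 2:1 and 4:1 in both directions.
- Reconcile 450 in the abstract with 550 in the Sample size calculation section, so that the expected 6-month number is stated once (236 or 289 at the stated losses).
- State the WHODAS 2.0 thresholds behind the three disability categories and make the 25%, 40% and 50% baseline risks consistent with one another.

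The cost is text and table edits, with no extra patients. The price is openness: the moderate or severe scenario will be seen to fall below 80% power. Reaching 80% would take 304/0.525 = 580 to 330/0.525 = 629 recruits at the stated losses (0.75 × 0.70 = 0.525; 1:1, no clustering). With recruitment fixed by funding, this should be reported as a limitation.
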